4.9.1 MAIN ANALYSIS

The primary analysis will use linear mixed models, with site as a random effect. We will compare change from baseline at 3 and 6 months between groups, with the baseline measurement included in the model as a covariate. The treatment effect will be presented as the mean difference between groups with the corresponding 95% confidence interval. Desaturation during 6MWT, although a stratifying factor in the design, will be modelled as a fixed effect.

The assumption of homogeneity of variance will be examined for each outcome by plotting residuals from the model against fitted values. Where right skewness results in heterogeneity of variance, a log transformation will be applied.

Missing data are anticipated for the primary outcome. The primary outcome is assumed to be missing-at-random (MAR), i.e. it is assumed that the probability of 3 month steps/day data being missing may depend on the values of the observed data, but not on the values of the missing data. Important explanatory and auxiliary variables such as age, type of ILD, respiratory function and extent of exertional desaturation are being collected and will be examined to assess the plausibility of the MAR assumption.

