2.2.3 PRIMARY OUTCOME

- Change from baseline in physical activity at 3 months, measured by the number of steps per day. Steps per day is measured using the StepWatch activity monitor (SAM) (Modus Health, Washington DC, USA). The SAM is worn on the ankle continuously for 7 days (except for bathing) at baseline, 3 months and 6 months. Days with < 8 hours recording or < 200 steps will be excluded. The mean number of steps per day will be calculated using the mean for all included days.

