2.4 RANDOMISATION AND BLINDING

Following baseline assessment participants are randomly allocated (1:1) to receive AOT or sham AOT (air) delivered by the Inogen One G3 HF POC. A computer generated, permuted block randomisation is used with stratification for (i) desaturation during 6MWT (<80% vs ≥80%) and (ii) site of recruitment. A remote, web-based, computer-generated randomisation procedure is used (provided by NHMRC Clinical Trials Centre).

Participants, clinicians and researchers will be blinded to group allocation. The Inogen One G3 HF POCs for AOT and air groups will be identical in appearance, display, weight and operation, with the only difference being the gas delivered. POCs were coded by the distributor, BOC, who have no involvement in trial conduct. All participants are advised against measuring oxygen saturation at home during the duration of the trial, as this does not represent usual clinical practice in any of the centres and may unblind the participants.

At the conclusion of the trial, participants are asked two questions to evaluate the success of blinding:

- Which treatment do you think you were receiving, oxygen or air?
- Did you have a pulse oximeter at home over the last 6 months? If yes, how did you use it?

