4.6 DATA SETS TO BE ANALYSED

All data will be analysed by intention to treat, including all randomised participants in the groups to which they were allocated, regardless of adherence.

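### As worded, the main model would drop any participant randomised without a valid baseline step mean, even with follow-up steps recorded, and the SAP gives no rule for keeping them

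*SAP*

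**What the plan says.** Section 2.2.3 defines the primary outcome: "Change from baseline in physical activity at 3 months, measured by the number of steps per day". On measurement it says: "The SAM is worn on the ankle continuously for 7 days (except for bathing) at baseline, 3 months and 6 months". Days are then filtered, "Days with < 8 hours recording or < 200 steps will be excluded", and averaged: "The mean number of steps per day will be calculated using the mean for all included days". It sets no minimum number of valid days and does not say what happens when none remains.

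On timing, 2.4 says: "Following baseline assessment participants are randomly allocated (1:1) to receive AOT or sham AOT (air) delivered by the Inogen One G3 HF POC". None of the eligibility criteria listed in 2.2.1 and 2.2.2 refers to step data.

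For the main analysis, 4.9.1 says: "We will compare change from baseline at 3 and 6 months between groups, with the baseline measurement included in the model as a covariate". Its missing-data paragraph assumes missingness at random, but spells this out only for steps at 3 months.

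On who is analysed, 4.6 says: "All data will be analysed by intention to treat, including all randomised participants in the groups to which they were allocated, regardless of adherence". Section 4.1 adds that the main analysis uses every outcome value available, under a named missing-data assumption, and that sensitivity analyses cover all individuals. Section 4.9.3 plans no other sensitivity analyses. Section 4.10 carries the same model, with the baseline value of each outcome as covariate, to the secondary outcomes.

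**The concern.** Baseline steps are needed twice in the 4.9.1 model: to compute the response and to supply the covariate. A participant with no valid baseline mean has neither. They would leave the analysis even if the 3- and 6-month recordings were complete.

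The analysed set would then be those with a usable baseline recording, not those randomised. Observed primary-endpoint data would be set aside because a pre-randomisation measurement is missing. The missing-data statement does not clearly cover this case, and no planned sensitivity analysis would bring these participants back. If the SAP stays silent, their handling would be decided at the analysis stage or left to the software default.

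**Working it through.** **1. Can a participant be without a baseline mean?** The baseline value is the mean over days that pass the 2.2.3 filter. One passing day is enough under the SAP's wording. With none, or with a failed monitor, the mean is undefined. Section 2.4 requires the baseline assessment to come first, but does not say that it must yield a usable step mean.

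**2. What does the model do with that participant?** Write B for baseline steps, Y for follow-up steps and T for arm. Section 4.9.1 fits

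Y − B = a + τT + βB + (desaturation) + (site) + error.

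If B is missing, both sides are undefined. As an illustration, this model was fitted at one follow-up visit to 260 simulated participants, 13 of them with baseline deleted, dropping incomplete rows. It kept 247; all 13 were lost although their 3-month steps were present. This shows how the model behaves, not how often it would happen in this trial.

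**3. Is the change format the cause?** Adding B to both sides gives

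Y = a + τT + (β + 1)B + (desaturation) + (site) + error.

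Only the baseline slope moves; τ is the same. With complete baselines, change and follow-up steps give the same treatment estimate. With Y as the response, the missing covariate alone would still remove the participant. What is needed is a rule for the missing baseline.

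**4. Reproducing the planned sample size.** Inputs from 2.5: difference 599, SD 1582, two-sided 5%, power 80%.

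n per group = 2 × (1.96 + 0.8416)² × (1582/599)² = 2 × 7.849 × 6.975 = 109.5, so 110 per group and 220 in total, as stated. Power at 110 per group is 80.2%.

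**5. Size of the loss.** The SAP gives no rate of missing baseline, so m is assumed. Analysable N = 260 × (1 − d) × (1 − m), where d is other loss. Two values of d bracket 2.5: 15.4% (1 − 220/260, implied by its targets) and 5% (the only rate it names, for starting long-term oxygen). Power = Φ(599 / (1582 × √(2/n)) − 1.96), with n = N/2.

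| Assumed m | N, d = 15.4% | Power | N, d = 5% | Power |
|---|---|---|---|---|
| 0% | 220 | 80.2% | 247 | 84.5% |
| 5% | 209 | 78.1% | 235 | 82.6% |
| 10% | 198 | 75.9% | 222 | 80.6% |

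At d = 15.4% the model would discard 11 participants at m = 5% and 22 at m = 10%, if all of them had follow-up steps. These figures use the plan's unadjusted two-group formula; they do not model the gain from baseline adjustment or repeated visits.

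**The case against.** The strongest reply is that the situation may never arise. Randomisation follows the baseline assessment, the 7-day wear is part of it, and one adequate day yields a baseline mean. Non-ambulant patients are excluded, so failing the 200-step filter on every day should be uncommon. The protocol may require a failed recording to be repeated before allocation. All of this stands. A reader might infer that the trial has randomised patients whom the analysis will discard; the SAP does not show that, and the number may be zero.

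A second reply is that no bias follows. Baseline steps are recorded before allocation, so exclusion on that ground does not by itself make the arms incomparable. This also stands. What is lost is precision and agreement between the declared and the actual analysis set.

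A third reply is that the outcome is defined as change, so without a baseline there is no outcome to analyse, and the general missing-at-random statement covers it. This softens the conflict with 4.1. It does not remove the conflict with 4.6, and 4.9.1 explains its assumption only for missing 3-month steps.

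Finally, the secondary outcomes are not all equally exposed. Eligibility requires a room-air 6-minute walk test, so a missing baseline walk distance should be rare. The wrist-accelerometer outcomes are the more likely place for the same problem.

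**Conclusion.** The point holds conditionally. Under 4.9.1 as worded, any participant randomised without a valid baseline step mean would be left out despite observed follow-up steps. That does not fit 4.6, sits badly with 4.1, and no planned analysis recovers them.

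The size depends on a rate the SAP does not give. If 220 would otherwise be analysable, 5% missing baseline costs about 2 percentage points of power and 10% about 4. If other loss is only 5% of the 260 randomised, power stays above the planned 80% even at 10% missing.

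Two stronger readings should be resisted. One is that the trial becomes underpowered: this depends on assumed rates and on ignoring the margin in the 260. The other is that the change-from-baseline format is itself the fault: the missing covariate would remove these participants with either response.

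**What to change.** In 4.9.1, make steps/day at 3 and 6 months the response, with baseline steps as covariate. Fill a missing baseline with the overall mean pooled over both arms, so that the filled value does not depend on allocation. A constrained longitudinal model, with baseline as a further response and baseline means set equal across arms, serves the same aim; name one method as the main analysis.

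State that everyone with a valid 3- or 6-month recording enters the main analysis, and report the number without a valid baseline by arm. Apply the same rule in 4.10, where it matters mainly for the two wrist-accelerometer outcomes.

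The cost is SAP wording, settled before unblinding, and a small change to the model code; no new data are needed. The downside is that participants with a filled baseline contribute slightly less precisely than those with a measured one. If every baseline is present, the filled-baseline model gives the same treatment estimate as the current one.

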2.2 PATIENT POPULATION

2.2.1 INCLUSION CRITERIA

- aged 18 years and over
- have a physician-confirmed diagnosis of fibrotic ILD, such as IPF, connective tissue disease-associated ILD, fibrotic hypersensitivity pneumonitis, idiopathic non-specific interstitial pneumonia, unclassifiable idiopathic interstitial pneumonia, environmental/occupational lung disease or sarcoidosis, with features of diffuse fILD of >10% extent on high-resolution CT, with ILD being the predominant pathological process (2)
- have had stable pharmacotherapy over the previous 3 months
- exhibit exertional desaturation, defined as oxyhaemoglobin saturation (SpO_2) $\leq 88\%$ for at least 10 consecutive seconds during a 6-minute walk test (6MWT) performed on room air.

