2.5 SAMPLE SIZE

A total of 220 participants (110 per group) would provide 80% power to detect, at the two-sided 5% level, a clinically important difference between groups in the primary outcome of 599 steps per day (3). This assumes an SD of 1582 steps, based on physical activity data previously collected at our centre in 52 patients with fILD

(4). Previous experience suggests that 5% of participants could start LTOT (and cease POC use) over 6 months. We therefore intended to randomise 260 participants to ensure that 220 participants completed the study.

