4 STATISTICAL ANALYSIS

4.1 GENERAL PRINCIPLES

- All outcomes and analyses are prospectively categorized as primary, secondary, or tertiary
- Summaries of continuous variables which are reasonably symmetrical will be presented as means and standard deviations, or as medians and inter-quartile ranges for skewed data. Categorical variables will be presented as frequencies and percentages.
- Differences in all endpoints between the two arms of the study will be tested independently at the two-tailed 0.05 level of significance. All estimates of treatment effects will be presented with 95% confidence intervals (CIs).
- Primary and secondary efficacy and safety outcomes analyses will be conducted on an intention-to-treat (ITT) basis so that all patients will be analysed in the group to which they were randomized irrespective of whether or not they received the allocated treatment.
- The ITT analysis strategy for PFOX is defined as follows:
 - Is based on an ITT design that aims to collect all outcome data on all randomized subjects;
 - Includes a main analysis that keeps subjects in their randomized groups, analyses all available outcome data, and is valid under a named plausible assumption about the missing data;
 - Includes sensitivity analyses that consider a range of plausible alternative assumptions that differ from the main assumption about the missing data;
 - All individuals are included in sensitivity analyses.
- For primary and secondary analyses, the treatment effect on the primary efficacy outcome will be adjusted for the baseline measurement of the outcome.
- Subgroup analyses will be carried out irrespective of whether there is a significant treatment effect on the primary outcome. Their purpose is to supplement evidence from the primary analysis to help to fully characterise the treatment effect. Results from subgroup analyses will be interpreted in this context.
- Analyses will be conducted primarily using R statistical software.

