4.7 PATIENT CHARACTERISTICS AND BASELINE COMPARISONS

In order to assess balance, description of the specified baseline characteristics will be presented for the Oxygen and Air groups (Table 1). Discrete variables will be summarized as frequencies and percentages. Unless otherwise indicated in the tables percentages will be calculated according to the number of patients for whom data are available. Continuous variables will be summarized by use of either mean and standard deviation or median and interquartile range. Durations and time intervals will be summarized by medians, IQRs, and ranges.

Baseline measures for patients will be presented by group for the following variables:

age, gender, body mass index, type of fibrosing ILD, respiratory function (FEV1, FVC and TLCO, absolute and %predicted), 6-minute walk distance (metres), resting SpO₂, nadir SpO₂ on 6MWT (%), % of waking hours with SpO₂ ≤ 88% during daily life, physical activity (average steps/day), Dyspnoea-12, KBILD, Hospital Anxiety and Depression Scale.

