4.9.2 SUBGROUP ANALYSES

No correction for multiple testing in subgroup analysis will be undertaken and multiplicity-unadjusted p-values will be reported, although the number of declared subgroup analyses will be specified in all publications.

The following subgroup analyses will be carried out for the primary outcome:

- Type of fibrosing ILD (IPF vs other)
- Severity of ILD (FVC<50% vs ≥50%predicted)

The effect of this factor will be assessed by adding an interaction term to the main model.

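### The primary model omits age, ILD type and respiratory function, which section 4.9.1 itself names as auxiliaries for its MAR assumption; the likely bias is small and the remedy almost free

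*SAP*

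**What the plan says.** SAP section 4.9.1 expects missing primary-outcome data. It assumes that missingness of 3-month steps may depend on observed values but not on the missing ones. It then refers to "Important explanatory and auxiliary variables such as age, type of ILD, respiratory function and extent of exertional desaturation", which are being collected and "will be examined to assess the plausibility of the MAR assumption". No other use in handling missing data is given.

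The model in the same section has site as a random effect, baseline steps as a covariate and 6MWT desaturation as a fixed effect. Of the four named variables, only desaturation is in it.

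Other sections that bear on this:

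- Section 4.1 promises a main analysis that "is valid under a named plausible assumption about the missing data", and also sensitivity analyses under alternative missing-data assumptions. Section 4.9.3, on other sensitivity analyses, says none is planned, and no other section specifies any.
- Section 4.9.2 uses ILD type, as "Type of fibrosing ILD (IPF vs other", and FVC only for subgroup interactions.
- Section 4.10 carries the same model factors over to the secondary outcomes.
- Section 4.7 already lists age, ILD type and "respiratory function (FEV1, FVC and TLCO, absolute and %predicted" among the baseline measures.

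**The concern.** A likelihood-based model fitted to the available data is protected when missingness depends on what the model conditions on. The SAP assumes MAR given a wider set of variables than its model contains. If age, ILD type or lung function drives both loss and steps, MAR in the SAP's sense can hold while the estimate is biased. The validity promised in 4.1 is then not secured for three of the four variables the SAP itself names.

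The planned examination does not close the gap. Relating missingness to observed covariates can show departure from MCAR, but it cannot separate MAR from MNAR. The plan also attaches no consequence to what the examination finds, so any later adjustment would be chosen after seeing the data.

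**Working it through.** **The plan's own figure.** Section 2.5 gives 599 steps/day, SD 1582, two-sided 5% and 80% power. n per arm = 2 × (1.960 + 0.842)² × (1582/599)² = 2 × 7.849 × 6.975 = 109.5, so 110 per arm and 220 in total. Power at 110 per arm is 80.2%. The figure reproduces.

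**Inputs.** From the SAP: SD 1582; 260 randomised (130 per arm); a loss allowance of (260 − 220)/260 = 15.4%. The SAP gives no missingness by arm, no dependence on a covariate and no covariate–outcome correlation, so these are assumed:

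- z is a standardised auxiliary variable, and r is its correlation with the outcome after the model covariates (0.1, 0.2, 0.3).
- Missingness is logistic in z, with log-odds 0.5 or 1.2 per SD, and participants with low z are lost more often. At 15.4% loss, slope 0.5 means 31% missing at −2 SD and 6% at +2 SD; slope 1.2 means 57% and 1%.
- 1582 is used as the residual SD.

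**Formula, no effect modification.** Bias = r × 1582 × (E[z | observed, oxygen] − E[z | observed, air]).

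Example: r = 0.3, slope 1.2 in both arms, loss 20% on air and 10% on oxygen. E[z | observed] is 0.1045 on oxygen and 0.1972 on air. Bias = 474.6 × (−0.0927) = −44.0. SE = 1582 × √(1/117 + 1/104) = 213.2. The ratio is 44.0/213.2 = 0.21 SE, and 44.0/599 = 7%.

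Size of bias in steps/day at r = 0.1 / 0.2 / 0.3. The direction understates oxygen when the air arm loses more low-z participants, and reverses if the arms are swapped.

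| Missingness pattern | Slope 0.5 | Slope 1.2 |
|---|---|---|
| Same slope and rate in both arms | 0 | 0 |
| Shared slope, 12% vs 8% | 3.0 / 6.1 / 9.1 | 6.1 / 12.2 / 18.3 |
| Shared slope, 18% vs 13% | 3.7 / 7.5 / 11.2 | 7.3 / 14.6 / 21.9 |
| Shared slope, 20% vs 10% | 7.5 / 15.0 / 22.5 | 14.7 / 29.3 / 44.0 |
| Slope in one arm only, 15.4% in both | 11.8 / 23.6 / 35.4 | 24.6 / 49.1 / 73.7 |
| Slope in one arm only, 20% vs 10% | 15.2 / 30.4 / 45.6 | 31.2 / 62.4 / 93.6 |

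The last cell is 93.6/213.2 = 0.44 SE, or 16% of 599.

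**Type I error.** Simulation of 20,000 trials per case at r = 0.3 gives:

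- 5.1% with the same pattern in both arms;
- 5.2% with shared slope 0.5, 20% vs 10%;
- 5.8% with shared slope 1.2, 20% vs 10%;
- 7.4% in the extreme one-arm case.

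With the driving covariates in the model, bias is within about 2 steps (Monte Carlo SE 1.5) and type I error is 4.9–5.3%.

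**Effect modification.** Suppose the treatment effect changes by 300 steps per SD of z (assumed), with identical 15.4% loss and slope 1.2 in both arms. Bias against the effect in all randomised participants is 300 × E[z | observed] = 300 × 0.1553 = 46.6 steps, or 0.22 SE. In 2 million simulated participants, adding z as a fixed covariate leaves about 47 steps. Imputing by arm from z leaves about 0.

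**FVC alone.** If TLCO drives the loss in the 44-step case, adjusting for FVC alone leaves about 40, 35 or 24 steps at FVC–TLCO correlations of 0.3, 0.5 and 0.7. Adding TLCO removes it.

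**The case against.** The strongest reply is that this is immaterial. Every driver is assumed. Section 2.4 states "Participants, clinicians and researchers will be blinded to group allocation", with devices identical in appearance, which makes strongly arm-specific dropout unlikely. Section 2.5 says "We therefore intended to randomise 260 participants to ensure that 220 participants completed the study"; that allowance concerns study completion, so 3-month loss may be lower. If 1582 is not adjusted for baseline, the biases in steps are overstated, although their ratio to the SE is not, because both scale with the SD. The model already holds baseline steps, desaturation and site, and the choice of further covariates is partly judgement in a plan marked final. All of this stands, and it limits the point to an optional improvement. It does not remove the mismatch between the assumption and the model.

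Three stronger readings are tempting and not supported.

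- A reader might infer that the primary analysis is seriously biased. Nothing in the SAP indicates the one-arm patterns needed for the largest figures.
- A reader might infer that the gap matters only when missingness differs by arm. That holds only without effect modification, and 4.9.2 plans to test interactions with ILD type and FVC.
- A reader might take 4.9.3 as settling that there is no missing-data sensitivity analysis. Section 4.1 promises such analyses, so the two sections conflict.

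**Conclusion.** The point holds as a modest one, worth considering. The model in 4.9.1 does not condition on three of the four variables the SAP names in support of its MAR assumption, and the planned examination cannot stand in for that. Bias arises if such a variable predicts both steps and missingness beyond the model covariates, and either missingness differs by arm or the variable modifies the treatment effect. Without either of these it is about 0.

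For correlations up to 0.3 and loss of about 10–20%, a shared slope gives at most 0.21 SE, and the extreme one-arm case 0.44 SE. Heavier assumptions give more: at r = 0.3, 20% vs 30% loss with odds ratios of 1 and 3 per SD gives 128 steps (0.60 SE). Nothing in the SAP points to such values. The secondary outcomes share the gap through 4.10.

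**What to change.** In 4.9.1, before unblinding:

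1. Add baseline age, ILD type (IPF or other), FVC % predicted and TLCO % predicted as fixed covariates of the primary model. Say how a missing baseline value is handled, for example the overall mean for a continuous measure. ILD type should be complete, because section 2.2.1 requires a "physician-confirmed diagnosis of fibrotic ILD, such as IPF, connective tissue disease-associated ILD" or a similar disease.
2. Add multiple imputation carried out separately by arm with the same variables. This also covers effect modification by them, which additive covariates do not.
3. State that this protects only against missingness that depends on those measures. IPF or other, FVC and TLCO represent ILD type and respiratory function only in part.
4. Describe the examination as a tabulation of missingness by arm against these variables, which can show departure from MCAR but cannot separate MAR from MNAR.
5. Reconcile 4.9.3 with the missing-data sensitivity analyses promised in 4.1.

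The cost is SAP wording and four model parameters on about 220 observations; the data are already listed in 4.7. If the covariates predict nothing, the SE rises from 213.3 to 215.3 (0.9%). With age, ILD type and FVC informative at r = 0.3, it fell from 212.1 to 205.1 in simulation (about 3%).
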